#### 12.1.1.3 General Considerations

For the determination of eligibility at Screening, only spirometry data obtained with the spirometer will be used.

To standardize spirometry across the two treatment arms, patients should not use a short-acting bronchodilator (e.g., albuterol) 2 hours prior to spirometry. If patients are on scheduled LABAs or LAMAs then the time from last dose to spirometry should be consistent throughout the study. Spirometry should ideally be performed before, or a minimum of 2 hours following the last inhalation of inhaled antifungals/antibiotics.

All inhaled medications, except investigational inhaled medications, are permissible during the trial and should be administered in the following order: inhaled bronchodilators, inhaled corticosteroids, inhaled antifungals/antibiotics, and then inhaled L-CsA.

Spirometry must always be performed before L-CsA inhalation.

#### 12.1.1.4 Onsite Visits

On-site spirometry should be performed by blinded personnel.

At every visit, spirometry will be measured using the column spirometers. Instructions for Use (including additional information on accuracy checks, cleaning of the device and further support) for both devices are available in the Study Manual. At least three acceptable and repeatable maneuvers on each device should be obtained at each visit.

At Visit 1, the spirometry at CCI post IMP will only be performed using the

Sufficient rest between both spirometry sessions should be granted to the subject at the Investigator's discretion. For the cel spirometry session, procedures identical to those to be used at home will be followed.

#### 12.1.1.5 Remote Visits

If patients cannot attend clinic visits due to COVID-19, remote visits using guided home spirometry may be performed (FEV1, or 5, and FVC) on the or device. For remote visits, the clinical trial personnel will telephone the patient and guide them through performing spirometry on the or device (for further assessments during remote visits, see Section 14.2.8).

Home spirometry should be scheduled around the same time as the usual clinic visits, whenever possible, to minimize the effects of circadian variation of lung function measurements.

In case measurements are not satisfactory after central overread, home spirometry may be repeated as close to the initially scheduled remote visit as possible.

#### 12.1.2 Progression of BOS

Due to the patchy distribution of affected areas in the pulmonary allograft, chronic rejection and BOS are not uniformly detectable by biopsy. This method has turned out to be too unspecific and harmful for routine diagnostic use. Therefore, non-invasive spirometry has been routinely

established using standardized airflow measurements which nowadays is used to determine FEV1 as a surrogate marker for the diagnosis of BOS, its classification and its control of progression.

Progression of BOS during the treatment period is defined as a further decline of  $FEV_1$  of  $\geq 10\%$  or  $\geq 200$  mL from Baseline  $FEV_1$  and absolute decrease in CCI of > 5% that is confirmed by measurements that are taken with CCI spirometer at least 2 weeks apart, OR worsening in BOS grade OR Re-transplantation, OR Death from respiratory failure. If a patient has an event which meets one of the criteria for progression of BOS, the Investigator should report the event via the eCRF.

#### 12.1.3 Augmentation or Change of Immunosuppression

Augmentation or change of immunosuppression/immunomodulation must be recorded in the eCRFs.

#### 12.1.4 Re-transplantation

Re-transplantation is defined as the date that a patient undergoes lung re-transplantation surgery. The reason for re-transplantation will be recorded. At the time of re-transplantation, the patient will be withdrawn from the study.

#### 12.1.5 Death

If a patient dies during the clinical trial, the medical monitor should be contacted as soon as is feasible. The cause of death and a clinical summary will be requested.

#### 12.1.6 Acute Rejection and its Severity

A patient with symptoms of a concomitant medical condition should be evaluated as clinically indicated. If a patient is diagnosed with acute rejection, the diagnosis should be recorded according to the following classification scheme. Any medications used to treat acute rejection should be recorded on the concomitant medication eCRF. The grade of acute rejection, airway inflammation, chronic airway rejection and chronic vascular rejection will be evaluated by the Investigator according to the revised working formulation for classification and grading of pulmonary allograft rejection [Stewart 2007] (Table 6):

Table 6. Revised Working Formulation for Classification and Grading of Pulmonary Allograft Rejection

A: Acute rejection	
Grade 0	None
Grade 1	Minimal
Grade 2	Mild
Grade 3	Moderate
Grade 4	Severe
B: Airway inflammation	
Grade 0	None
Grade 1R	Low grade
Grade 2R	High grade
Grade X	Ungradable
C: Chronic airway rejection – obliterative bronchiolitis	
0	Absent
1	Present
D: Chronic vascular rejection – accelerated graft vascular sclerosis	

"R" denotes revised grade to avoid confusion with 1996 scheme.

#### 12.1.7 Antibody-Mediated Rejection

While less common in patients more than one-year post-transplant, if the treating physician makes the diagnosis of antibody-mediated rejection (AMR), this should be recorded in the eCRF. The diagnostic criteria and a working consensus definition established by the ISHLT with the aim of determining criteria for pulmonary AMR and establishing a definition should be used to support the diagnosis [Levine 2016]. See Appendix III for further information on Antibody-Mediated Rejection.

#### 12.1.8 Quality of Life Questionnaire (EQ-5D-5L)

The EQ-5D-5L is a standardized measure of health status developed by the EuroQol Group in order to provide a simple, generic measure of health for clinical appraisal. Patients will be asked to manually complete the EQ-5D-5L at Visits 1, 4, 6, and 9/EoT and results will be entered into the eCRFs by site staff.

#### 12.1.9 Hospitalizations

Hospitalizations for any reason other than a scheduled procedure should be considered as serious adverse event and should be recorded in the eCRFs with admission date, discharge date, reason for admission, and additional diagnoses. If a patient requires mechanical ventilation for any reason other than a planned surgical procedure, dates of mechanical ventilation, and reason for mechanical ventilation should be recorded separately. A Hospitalization Discharge Summary may be requested by the Medical Monitor and shared with the DMC and/or AC.

#### 13 ASSESSMENT OF SAFETY

#### 13.1 Safety Parameters

Safety Assessments at every visit include physical examination, vital signs, adverse event reporting, and clinical laboratory parameters (performed at the local labs in each study site).

Acute tolerability of IMP during initial dosing will be assessed by spirometry before and after inhalation.

COVID-19 specific consideration: In case the planned on-site visit cannot be performed, the PI or the Sub-Investigator and/or an appropriately qualified site study team member must call the patient to assess any potential adverse events (AEs) and to confirm the patient's status and wellbeing (see also Section 14.2.8).

#### 13.1.1 Adverse Events (AEs)

#### 13.1.1.1 Definitions

Adverse Event (AE)

An AE is any untoward medical occurrence in a patient after administration of a pharmaceutical product and which does not necessarily have a causal relationship with this treatment. An AE can therefore be any unfavorable and unintended sign (including an abnormal laboratory finding), symptom, or disease temporally associated with the use of a medicinal (investigational) product, whether or not related to the medicinal (investigational) product (ICH Guidelines for Good Clinical Practice, E6(R2), 9 November 2016).

This includes worsening of a pre-existing condition or increase in frequency of a pre-existing condition. An adverse event is considered serious if it meets any of the serious criteria listed below. To ensure no confusion or misunderstanding of the difference between the terms "serious" and "severe", which are not synonymous, the following clarification is provided:

The term "severe" is often used to describe the intensity (severity) of a specific event (as in mild, moderate, or severe myocardial infarction); the event itself, however, may be of relatively minor medical significance (such as severe headache). This is not the same as "serious", which is based on patient/event outcome or action criteria usually associated with events that pose a threat to a patient's life or functioning. Seriousness (not severity) serves a guide for defining regulatory reporting obligations.

The official definition also extends to AEs occurring during the off-treatment follow-up period.

Each patient will be closely observed and questioned for AEs during the clinical trial period with non-leading questions (e.g., how do you feel?). The patients will be instructed to report to the clinical trial staff immediately any symptoms and/or signs which occur between the scheduled observation times.

All AEs reported by the patient or observed by the Investigator or hospital personnel will be documented in the respective eCRF. The following information regarding each adverse event will be obtained: date and time of onset and resolution (duration), serious or non-serious (as defined below), severity, treatment required, outcome, relationship to certain medication, and if the AE caused withdrawal from the clinical trial.

In addition to the Investigator's own description of the AE, each AE event will be coded by data management according to the Medical Dictionary for Regulatory Activities (MedDRA) code list. The verbatim term will be recorded in the eCRF.

Abnormal laboratory test results will be reported as AEs if they are indicative of a clinical condition that meets the criteria for an AE.

#### Adverse Drug Reaction (ADR)

Adverse drug reactions (ADRs) are all noxious and unintended responses to a medicinal product related to any dose that a causal relationship between the medicinal product and an adverse event is at least a reasonable possibility, i.e., the relationship cannot be ruled out. An unexpected ADR is any adverse reaction not identified in nature, frequency, or intensity in the current Investigator's Brochure.

#### Serious Adverse Event (SAE)

Each adverse event is to be classified by the Investigator as SERIOUS or NON-SERIOUS.

The International Conference on Harmonisation (ICH) of Technical Requirements for Registration of Pharmaceuticals for Human Use defines a serious adverse event as any adverse event occurring at any dose that results in any of the following outcomes:

- Death
- A life-threatening event (immediate risk of death at the time of the event)
- Inpatient hospitalization or prolongation of existing hospitalization
- A persistent or significant disability/incapacity
- A congenital anomaly/birth defect
- Other important medical event (Medical and scientific judgment should be exercised in deciding whether expedited reporting is appropriate in other situations, such as important medical events that may not be immediately life-threatening or result in death or hospitalization but may jeopardize the patient or may require intervention to prevent one of the other outcomes listed in the definition above. These should also usually be considered serious.)

#### 13.1.1.2 Relationship to Clinical Trial Treatment Assignment

All adverse events will be evaluated by the Investigator for potential relationship to the clinical trial treatment assignment (L-CsA plus SoC or SoC alone) in the following categories:

- **Unrelated**: An AE for which there is no evidence of any causal relationship with the clinical trial treatment assignment
- **Possible**: An AE that might be due to the use of the clinical trial treatment assignment. An alternative explanation, e.g., concomitant drug(s), concomitant disease(s), is inconclusive. The relationship in time is reasonable; therefore, the causal relationship cannot be excluded.
- **Definite**: An adverse event that follows a reasonable temporal sequence from administration of the clinical trial treatment assignment; that follows a known or expected response pattern to the suspected clinical trial treatment assignment.

#### 13.1.1.3 Maximum Intensity

All adverse events will be graded according to the following:

- **Mild**: Event requiring no special treatment and generally does not interfere with usual activities.
- **Moderate**: Event that impairs usual activities but may be ameliorated by simple therapeutic maneuvers.
- Severe\*: Event which impairs usual activities and requires intervention.
- \* There is a distinction between a severe adverse event and a serious adverse event; a severe reaction is not a serious adverse event unless it meets one of the criteria for serious events (see Section 13.1.1.1).

[figure not shown]
## 13.1.1.4 Serious Adverse Event (SAE) Reporting Any serious adverse events occurring

- between the first clinical trial procedure after obtaining informed consent and within 4 weeks
  after the completion of the EoT visit, whether or not considered related to the clinical trial
  treatment assignment
- at any time after completion of the last follow-up and coming to the attention of the Investigator, if it is judged as related to the patient's participation in the clinical trial

#### must be reported to CCI IMMEDIATELY, but within 24 hours upon knowledge, as follows:

- Document the event in the eCRF within 24 hours of discovery
- Submit the SAE report by FAX or e-mail it to a list of predefined recipients.
- Follow-up the SAE until the outcome is determined, providing periodic updates in the eCRF
- Provide any additional information if requested

Contacts of ccl are as follows:

#### Timelines for Suspected Unexpected Serious Adverse Reaction (SUSAR) reporting to Competent Authorities and IRBs/ECs

All suspected unexpected serious adverse reactions (SUSARs) will be reported by the Sponsor to the Competent Authorities and to the IRBs/ECs concerned as soon as possible, but within a maximum of 15 days (fatal or life-threatening SUSARs within a maximum of 7 days) of first knowledge.

Relevant follow-up information of fatal or life-threatening SUSARs will be communicated subsequently within an additional eight days.

#### 13.1.1.4.2 Other Events to be Treated as Serious Adverse Events Exposure to drug during pregnancy/lactation:

L-CsA:

In principle, pregnancy and the lactation period are exclusion criteria. In the event of a pregnancy occurring during the course of the clinical trial, the patient must be withdrawn from all IMP treatment immediately and permanently. The Sponsor must be notified without delay and the patient followed during the entire course of the pregnancy and postpartum period. Prenatal and neonatal outcomes must be recorded even if they are completely normal and without AEs. The SAE reporting procedure should be followed, even though pregnancy is not considered an SAE. No "serious criterion" should be checked. The SAE report form is solely used to ensure expedited reporting.

If any clinical trial patient becomes pregnant during the study period, the Investigator must contact Zambon SpA as the Sponsor of the clinical trial or its designee to discuss the management of the patient.

#### 13.1.1.4.3 Investigational Medicinal Product (IMP) Overdosing

An overdose is a deliberate or inadvertent administration of a treatment at a dose higher than specified in the protocol. For the purposes of this clinical trial, any dose of aerosolized IMP administered to a patient that exceeds the dose foreseen in the protocol by more than 50% over 4 weeks should be reported as an overdose.

The Investigator/Sponsor responsibilities in regard to reporting SAEs are in accordance with the US Food and Drug Administration and other Competent Authorities concerned.

13.1.1.4.4 Events not Regarded as Adverse Events/Serious Adverse Events

The following events will be not regarded as AEs/SAEs:

- Pre-scheduled (before any trial-related activities commenced) hospitalizations/surgeries/ interventions
- Trial endpoint-related worsening; this will be assessed in the endpoint analysis.

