#### 15.3 Adverse Events

All AEs occurring during the clinical trial, whether or not attributable to study treatment, will be documented in the eCRF. All AEs will be coded to SOCs and PTs using the MedDRA dictionary (version 23.1).

Treatment-emergent adverse events (TEAEs) are defined as AEs with onset on or after the date of randomization.

The Investigator will assess the relationship (unrelated, possible, definite) of each AE to the clinical trial treatment assignment (L-CsA plus SoC or SoC alone). Treatment-related AEs are defined as events the Investigator considers to be possibly or definitely related to clinical trial treatment assignment.

All AEs reported in the eCRF will be presented in by-patient listings for the SAF.

The following summaries will be presented for AEs by treatment group and overall:

- Overview table including the number and percent of patients with:
  - o AEs,
  - o TEAEs.
  - o TEAEs leading to discontinuation of study treatment,
  - o TEAEs leading study discontinuation,

Final Version 5.0 Page 61 of 76

- o TEAEs leading to death.
- o TEAEs by severity (Mild, Moderate, Severe),
- o Study treatment related TEAEs,
- o Serious TEAEs,
- Serious study treatment related TEAEs;
- TEAEs, grouped within SOC by decreasing frequency of PT;
- TEAEs by decreasing frequency of PT;
- TEAEs leading to discontinuation of study treatment, grouped within SOC by decreasing frequency of PT;
- TEAEs leading to study discontinuation, grouped within SOC by decreasing frequency of PT;
- TEAEs leading to death, grouped within SOC by decreasing frequency of PT;
- TEAEs by maximum severity, grouped within SOC by decreasing frequency of PT;
- TEAEs by relationship, grouped within SOC by decreasing frequency of PT;
- Serious TEAEs, grouped within SOC by decreasing frequency of PT;
- Related serious TEAEs, grouped within SOC by decreasing frequency of PT.

Patients who have multiple events coded to the same PT or within the same SOC will be counted only once in the patient counts for the corresponding summaries, but all events will be considered and listed. Table presentations will contain counts of patients, percentages of patients, and the number of events.

Any AE with missing relationship will be assumed related and summarized in the possible related category to clinical trial treatment assignment. Patients who experience the same event multiple times will be included in the most related category for summarization.

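### The undefined exemption of endpoint-related worsening from AE and SAE reporting conflicts with the hospitalization rule and the AE definition, so admissions caused by BOS worsening may or may not reach the safety tables

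*Protocol*

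**What the plan says.** Protocol 13.1.1.4.4 opens its list with "The following events will be not regarded as AEs/SAEs". One of its two entries covers pre-scheduled admissions and procedures. The other is "Trial endpoint-related worsening; this will be assessed in the endpoint analysis". The protocol does not say which endpoint or what degree of worsening is meant, or what applies when the worsening is fatal, life-threatening or leads to admission.

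Other sections bear on the same events:

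- Protocol 13.1.1.1, on what counts as an AE: "This includes worsening of a pre-existing condition or increase in frequency of a pre-existing condition".
- Protocol 13.1.1.1, on SAEs: any adverse event "occurring at any dose that results in any of the following outcomes", with death and inpatient hospitalization among the outcomes. It makes no endpoint exception.
- Protocol 13.1.1.4: SAEs are reported within 24 hours whether or not they are thought related, again with no endpoint exception.
- Protocol 12.1.9: "Hospitalizations for any reason other than a scheduled procedure should be considered as serious adverse event".
- Protocol 12.1.2: BOS progression is a confirmed spirometric decline, "OR worsening in BOS grade OR Re-transplantation, OR Death from respiratory failure".

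The SAP neither repeats nor reverses the exemption. Its fatal-event summary in Section 15.3 is "TEAEs leading to death, grouped within SOC by decreasing frequency of PT", and its serious-event summaries are likewise built from TEAEs.

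**The concern.** BOS worsening is the disease course under study, so the exempted category is likely to include serious events. If one site files an SAE for an admission caused by falling lung function and another treats it as endpoint worsening, the serious TEAE table partly measures site interpretation. The trial is open-label, and under Protocol 13.3 the investigator has the final decision on whether an event is progression. The adjudication committee reviews only after a patient has finished the study. No blinded check therefore exists when the reporting choice is made.

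Three things depend on AE status: 24-hour reporting, the causality assessment in Protocol 13.1.1.2, and entry into the TEAE tables. The protocol also describes a decline in FEV1 with symptoms as a sign of intolerability of the inhaled product (Protocol 10.3.1.1 and 13.1.2). A drug-related decline later in the trial could be filed as endpoint worsening and never be assessed for causality.

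**Working it through.** The point rests on no power, alpha or sample-size figure, so the check is textual. Take three kinds of event and apply each rule.

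| Event | Protocol 13.1.1.4.4 | Other rules |
|---|---|---|
| FEV1 decline or BOS grade change, no admission | Not an AE | AE under 13.1.1.1 |
| Unscheduled admission caused by BOS worsening | Exempt if the exemption follows the cause of admission; silent otherwise | SAE under 12.1.9; meets a seriousness outcome in 13.1.1.1 |
| Respiratory death or re-transplantation | Exempt only if the term means the whole progression definition | Death is a seriousness outcome in 13.1.1.1; SAEs are reportable under 13.1.1.4 |

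**Row 1.** A list of exceptions after a general definition can be read as a carve-out. The wording conflicts, but a site could reasonably give the exception precedence.

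**Row 2.** This is the direct contradiction. Protocol 12.1.9 is itself a specific rule, and its only exception is a scheduled procedure. That matches the pre-scheduled entry in 13.1.1.4.4 but not the worsening entry. The rules agree only if the exemption is taken to cover the measured decline and not the admission it causes, which the protocol does not say.

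**Row 3.** The result depends on the meaning of worsening. Protocol 12.1.2 uses the word for one component: "worsening in BOS grade OR Re-transplantation, OR Death from respiratory failure". Read that way, death and re-transplantation stay outside the exemption. Read as anything counted in the trial's progression endpoint, they fall inside it.

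**Downstream.** SAP 15.3 draws its serious and fatal tables from AEs with onset on or after randomization, so an event never recorded as an AE cannot appear. The legible safety sections (SAP 15.1 to 15.8) contain no by-arm table of all deaths, re-transplantations or hospitalizations independent of AE status.

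**Size.** The documents give no expected rate of respiratory death, re-transplantation or worsening-related admission. For scale only, assume a combined rate r of respiratory death or re-transplantation among the 169 randomized patients (SAP 8.2). The most events that could be left out, on the broad reading, is 169 × r:

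- r = 2%: 169 × 0.02 = 3.38, about 3
- r = 5%: 169 × 0.05 = 8.45, about 8
- r = 10%: 169 × 0.10 = 16.9, about 17
- r = 15%: 169 × 0.15 = 25.35, about 25

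These rates are assumptions, and the counts are ceilings rather than estimates of loss.

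**The case against.** A reader might infer that sites need not report respiratory deaths and re-transplantations, so that the gravest events will leave the safety record. The documents do not support that as a statement of fact, for these reasons:

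- Protocol 12.1.2 keeps worsening of grade apart from re-transplantation and death, and the primary endpoint is FEV1 change. A reading limited to functional decline is natural.
- SAP 9.2.4 cites an end-of-study withdrawal reason that groups death with adverse events, and SAP 15.3 plans a table of fatal TEAEs. Some deaths are clearly expected to be recorded as AEs.
- The events are captured elsewhere. The synopsis covers overall, BOS-related and other mortality as well as hospitalization days. Progression is reported through the eCRF (Protocol 12.1.2), the reason for re-transplantation is recorded (12.1.4) and the cause of death is requested (12.1.5). SAP 14.1.1 and 14.1.3 enter death and re-transplantation as an FEV1 of zero.
- The DMC is unblinded and receives FEV1 (Protocol 13.2). Its charter and separate SAP are not available, so an undercount in its reports cannot be asserted.
- Parts of the SAP's efficacy section are redacted and may already tabulate mortality or hospitalization.
- Harm around first dosing has its own route: SAP 15.4 summarizes post-dose spirometry and treats cough and dyspnea as AEs. Protocol 9.4.3 covers later intolerance and requires the reason for stopping or adjusting L-CsA to be documented.

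Most of this stands, and it confines the death and re-transplantation issue to a broad reading. It does not resolve the conflict over worsening-related admissions. The other capture routes also do not supply SAE reporting, causality assessment or entry to the TEAE tables. The gap for drug-related decline is narrower than it might appear: mainly later decline without symptoms.

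**Conclusion.** The concern holds as a contradiction in the reporting rules. For an unscheduled admission caused by BOS worsening, Protocol 13.1.1.4.4 can be read to exempt what 12.1.9 requires and 13.1.1.1 includes, and the SAP safety tables inherit whichever choice the site made. For respiratory death and re-transplantation the documents leave the loss possible on a broad reading, but do not show that it will happen.

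The number of events affected cannot be determined. A reader might also infer that the arms will be undercounted differently. Open-label conduct and the investigator's final say make that possible, but nothing in the documents shows its direction or size. The conclusion assumes that no unseen document, such as the eCRF guidelines or the DMC charter, defines the term, and that no redacted section already provides a table independent of AE status. It deserves action before database lock but does not affect the primary analysis.

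**What to change.** **Protocol.** Reconcile Sections 12.1.2, 12.1.9, 13.1.1.1, 13.1.1.4 and 13.1.1.4.4. Define endpoint-related worsening, and state whether an endpoint event that meets a seriousness criterion remains reportable as an SAE.

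**SAP.** This is the main change, because SAP version 5.0 (27 March 2024) already records 169 patients as randomized and a protocol clarification comes late for most of their data. Before database lock:

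1. Collect deaths, re-transplantations and unscheduled hospitalizations from every eCRF source: adverse events, hospitalization records, end-of-study form and progression reports.
2. Reconcile them against the SAE database in a listing that flags each event absent from it, and query the sites.
3. Add a table by arm of these three event types, whatever their AE status, beside the TEAE tables in Section 15.3. If a redacted section already holds such a table, cross-refer to it.

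The cost is a protocol clarification, one listing, one table and some retrospective site queries. Treatment, data collection at visits and the primary analysis do not change. The safety counts for these events would then no longer depend on how each site read the exemption.
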